8.4 Minimal Evaluation Visits (all subjects)

After V1 for subjects entering from N01379, V2 will not be conducted). Subsequent visits will be conducted according to the visit schedule provided in [Table 5-3](#).

At the Minimal Evaluation Visits (MEV) assessments are as follows:

- Vital signs
- Body weight
- IVRS/IWRS
- Subject's DRC dispensed
- Subject's DRC retrieval
- Seizure counts (collected on the subject's DRC on a daily basis)
- Urine pregnancy test (if applicable)
- Liver function tests will be performed in V4 (M) and V6 (M 9) as described in [Section 10.2](#).
- AE reporting
- C-SSRS
- Medical procedures

- Concomitant AEDs
- VNS settings
- Concomitant non-AEDs
- Study drug dispensing
- Study drug return/accountability

8.5 Full Evaluation Visits (all subjects)

After V1 for subjects entering from N01379, V3 will not be conducted. Subsequent visits will be conducted according to the visit schedule provided in Table 5–2.

At the Full Evaluation Visits (FEV) assessments are as follows:

- Vital signs
- Body weight
- Physical examination
- Neurological examination
- 12-lead ECG
- IVRS/IWRS
- Subject's DRC dispensed
- Subject's DRC retrieval
- Seizure counts (collected on the subject's DRC on a daily basis)
- Laboratory safety assessments including hematology, blood chemistry, urinalysis and urine pregnancy test (if applicable)
- AE reporting
- C-SSRS
- Medical procedures
- Concomitant AEDs
- VNS settings
- Concomitant non-AEDs
- Study drug dispensing
- Study drug return/accountability

8.6 Yearly Evaluation Visit (all subjects)

At the Yearly Evaluation Visit (YEV) assessments are as follows:

- Vital signs
- Body weight

- Physical examination
- Neurological examination
- 12-lead ECG
- IVRS/IWRS
- Subject's DRC dispensed
- Subject's DRC retrieval
- Seizure counts (collected on the subject's DRC on a daily basis)
- Laboratory safety assessments including hematology, blood chemistry, urinalysis and urine pregnancy test (if applicable)
- AE reporting
- C-SSRS
- Medical procedures
- Concomitant AEDs
- VNS settings
- Concomitant non-AEDs
- Study drug dispensing
- Study drug return/accountability

8.7 End of Study Visit or Early Discontinuation Visit (all subjects)

At the End of Study Visit or Early Discontinuation Visit (EDV) assessments are as follows:

- Vital signs
- Body weight
- Physical examination
- Neurological examination
- 12-lead ECG
- IVRS/IWRS
- Subject's DRC dispensed
- Subject's DRC retrieval
- Seizure counts (collected on the subject's DRC on a daily basis)
- Laboratory safety assessments including hematology, blood chemistry, urinalysis and urine pregnancy test (if applicable)
- AE reporting
- C-SSRS

- Medical procedures
- Concomitant AEDs
- VNS settings
- Concomitant non-AEDs
- Study drug dispensing
- Study drug return/accountability
- End of study status (end of study status will be completed at the End of Study Visit for subjects who will be converted without down-titration to commercial BRV if, when, and where available).

8.8 Final Visit (all subjects)

At the Final Visit (FV) assessments are as follows:

- Vital signs
- Body weight
- Physical examination
- Neurological examination
- 12-lead ECG (mandatory, except if the FV follows an EDV where ECG results were normal)
- IVRS/IWRS
- Subject's DRC retrieval
- Seizure counts (collected on the subject's DRC on a daily basis)
- Laboratory safety assessments (mandatory, except if the FV follows an EDV where laboratory results were normal): hematology, blood chemistry, urinalysis, and urine pregnancy test (if applicable)
- AE reporting
- C-SSRS
- Medical procedures
- Concomitant AEDs
- VNS settings
- Concomitant non-AEDs
- Study drug return/accountability
- End of study status

The FV is not applicable to subjects who convert to commercial BRV (if, when, and where available).

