5.1.1 Study duration per subject

The following study periods are defined:

- Screening Visit (Visit 0, up to 3 weeks before the Entry Visit (EV) for direct enrollers in Japan only)
- Evaluation Period (Visit 1 to End of Study Visit or Early Discontinuation Visit [EDV]): Subjects who enroll in EP0083 and N01379 will enter the Evaluation Period.
- Down-Titration Period (up to 4 weeks)
 - If the subject is discontinuing study drug, the Investigator will first plan an EDV followed by the progressive down-titration of study drug.
 - During the Down-Titration Period, the BRV dose may be decreased in steps of a maximum of 50mg/day on a weekly basis. A last down-titration step at 25mg/day for 1 week should be included prior to the 2-week Study Drug-Free Period.
- 2-week Study Drug-Free Period: After completion of the Down-Titration Period, or for those subjects who for extenuating circumstances do not complete a Down-Titration Period, the subject will be required to enter a 2-week Study Drug-Free Period, followed by a Final Visit (FV).

Visits should occur on the specified Visit/Week. A ± 7 day window for each specified Visit/Week is allowed, provided the subject has adequate investigational medicinal product (IMP) to sustain the visit window. The end of the study is defined as the date of the last visit of the last subject in the study.

EP0085 will continue until the market approval of BRV, or until the sponsor decides to close the study, whichever comes first. In the event that market approval is not requested or obtained in the participant country, the subject will be able to continue in EP0085 for two years after entering EP0085.

In Japan, EP0085 will continue as a postmarketing clinical study until approximately 6 months after the date of BRV approval for the partial seizure indication.

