Visit	V1	V2 ^a , V4, V6, V8, V10…	V3 ^a , V5, V9…	V7, V11…	NA	NA
Month	M0	M1, M3, M9, M15, M21…	M2, M6, M18…	M12, M24…	NA	NA
Week	W0	W4, W12, W36, W60, W84…	W8, W24, W72…	W48, W96…	NA	NA

Note: For subjects who have completed EP0083 or N01379, assessments marked (*) should have already been completed during the last visit of the previous protocol and do not need to be repeated at Visit 1.

^a After Visit 1, for subjects entering from N01379 V2 and V3 will not be conducted. Subsequent visits will be conducted according to the visit schedule provided in Table 5–3.

^b Informed consent must be obtained during the previous study.

^c General medical and procedures history, AED history, and epilepsy history will be obtained from the Baseline of EP0083 or Baseline of N01358 (for subjects entering from N01379) and do not need to be recorded on the eCRF for this study.

^d Height will be recorded at V1 only.

^e At the FV, a 12-lead ECG is mandatory, except if the FV follows an EDV where ECG results were normal.

^f Seizure counts are collected on the subject's daily record card on a daily basis.

^g Laboratory safety assessment will not be performed at MEV. Only liver function tests will be performed at the MEV in Visit 4 (M3) and Visit 6 (M9). Laboratory safety assessment is mandatory at the FV, except if the FV follows an EDV where laboratory results were normal. The result of the calculated creatinine clearance will be provided by the central laboratory.

^h A urine pregnancy test will be done for female subjects with childbearing potential.

ⁱ End of study status will be completed at the FV for subjects having performed an EDV and down-titration of BRV (discontinued subjects) and for subjects leaving the study at the end of the program (completed subjects). Alternatively, end of study status will be completed at the End of Study Visit for subjects who will be converted without down-titration to commercial BRV if, when, and where available.

Table 5-2: Schedule of study assessments for subjects directly enrolled into EP0085 in Japan

Assessments	SV	EV	MEV	FEV	YEV	End of Study Visit or EDV	FV
Visit	V0	V1	V2, V4, V6, V8, V10...	V3, V5, V9...	V7, V11...	NA	NA
Month	-	M0	M1, M3, M9, M15, M21...	M2, M6, M18...	M12, M24...	NA	NA
Week	(-2 to -21 days)	W0	W4, W12, W36, W60, W84...	W8, W24, W72...	W48, W96...	NA	NA
Written informed consent	X						
Subject identification card dispensed	X						
Eligibility assessment	X	X					
Demography	X						

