^c If no appropriate EEG result (within the last 10 years) is available, the EEG must be scheduled at the SV and the results received before the EV.

^d A neuro-imaging procedure (brain magnetic resonance imaging/brain computerized tomography scan or any other imaging test) should be performed if no report is available within the previous 2 years. If there is not a known history and clinical signs or suspicion of brain tumor, performing a neuro-imaging procedure for the purpose of the study is not mandatory. If the investigator can judge a participant's eligibility by his/her own medical judgement without performing neuro-imaging procedure, it is also acceptable. However, if the etiology of epilepsy is a brain tumor, or the participant has any intracranial structural abnormality as documented by a previous neuro-imaging procedure, the participant needs to have documentation of a neuro-imaging procedure which is no older than 2 years.

^e At the SV and EV (For DE), historical seizure information (including type, frequency, and date) should be checked. Historical seizure information must have been prospectively recorded on a subject's own document (eg, DRC). After the EV, seizure counts are collected on the subject's DRC on a daily basis

^f Laboratory safety assessment will not be performed at MEV. Only liver function tests will be performed at the MEV in Visit 4 (M3) and Visit 6 (M9). Laboratory safety assessment is mandatory at the FV, except if the FV follows an EDV where laboratory results were normal. The result of the calculated creatinine clearance will be provided by the central laboratory.

^g At the SV, a serum pregnancy test will be performed for female subjects with childbearing potential. At all subsequent visits, a urine pregnancy test will be performed

^h Concomitant levetiracetam is permitted for directly enrolled subjects in Japan, but not allowed for subjects transitioning from EP0083 and N01379.

Table 5-2: Schedule of study assessments for subjects directly enrolled into EP0085 in Japan

Assessments	SV	EV	MEV	FEV	YEV	End of Study Visit or EDV	FV
Visit	V0	V1	V2, V4, V6, V8, V10...	V3, V5, V9...	V7, V11...	NA	NA
Month	-	M0	M1, M3, M9, M15, M21...	M2, M6, M18...	M12, M24...	NA	NA
Week	(-2 to -21 days)	W0	W4, W12, W36, W60, W84...	W8, W24, W72...	W48, W96...	NA	NA

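### Section 8.8 lets the Final Visit urine pregnancy test lapse after a normal Early Discontinuation Visit, although Tables 5-1 and 5-2 require it

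*Protocol*

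**What the plan says.** The protocol gives two rules for the urine pregnancy test at the FV.

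**Procedure text.** Section 8.8 has a single laboratory item, mandatory "except if the FV follows an EDV where laboratory results were normal): hematology, blood chemistry, urinalysis, and urine pregnancy test (if applicable"). The pregnancy test is in the list that the waiver governs. Section 10.2 supports this reading: it counts the pregnancy test among the laboratory safety assessments and repeats the FV waiver for those assessments.

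**Schedules.** Tables 5-1 and 5-2 each give the pregnancy test its own row, marked at the FV. The waiver sits in a footnote to the laboratory row only (g in Table 5-1, f in Table 5-2): "Laboratory safety assessment is mandatory at the FV, except if the FV follows an EDV where laboratory results were normal". The footnotes to the pregnancy row contain no exception. Table 5-1 footnote h says "A urine pregnancy test will be done for female subjects with childbearing potential". Table 5-2 footnote g, after describing the serum test at screening, says "At all subsequent visits, a urine pregnancy test will be performed".

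**Neighbouring visits.** Section 8.4 lists "Urine pregnancy test (if applicable") as an item of its own, at visits with no full laboratory panel. Section 8.7 includes the test at the EDV, within "Laboratory safety assessments including hematology, blood chemistry, urinalysis and urine pregnancy test (if applicable"). Study drug is also dispensed at that visit. Section 8.8 adds that "The FV is not applicable to subjects who convert to commercial BRV".

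**The concern.** A site cannot tell which rule applies, and the rule in Section 8.8 does not suit this test. Waiving a repeat of hematology, chemistry and urinalysis after normal results is reasonable. Those results carry no information about pregnancy, and a negative pregnancy test at the EDV does not exclude a conception just before that visit or in the weeks after it, when the woman may still be taking brivaracetam.

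Under Section 8.8 the EDV test is the last scheduled one for a woman of childbearing potential whose EDV results were normal. Section 10.1.4 requires notification, and follow-up to outcome, for a pregnancy after first intake of study drug, but only once the investigator learns of it. The FV is the last scheduled opportunity to find one that nobody suspects. What is at stake is subject safety and complete reporting of exposed pregnancies. No efficacy or safety endpoint is affected: SAP Section 9.3.1.1 lists pregnancy test results and does not summarize them.

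**Working it through.** The plan gives no figure of its own on this point. The check compares the texts and then derives the untested interval.

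**1. Comparison of the texts**

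| Place | Pregnancy test at FV after a normal EDV |
|---|---|
| Section 8.8 | Inside the waived laboratory item: not mandatory |
| Section 10.2 | Counted as a laboratory safety assessment, same waiver: not mandatory |
| Table 5-1 (rollover subjects) | Own row, marked at FV, no waiver: required |
| Table 5-2 (direct enrollers) | Own row, marked at FV, urine test at every visit after screening: required |

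All four are current text, so the conflict is real and applies to both rollover and directly enrolled subjects.

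**2. Who is affected**

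Only women of childbearing potential whose FV follows an EDV with normal laboratory results. Women who convert to commercial brivaracetam have no FV. Women with abnormal EDV results get no waiver. Completers whose FV follows an End of Study Visit are, read literally, also outside it, because the waiver names only the EDV.

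**3. Interval from the EDV test to the FV**

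Inputs from Protocol Section 5.1.1: steps of at most 50 mg/day per week, a last week at 25 mg/day, and then a 2-week drug-free period. That section also allows "for those subjects who for extenuating circumstances do not complete a Down-Titration Period" to go straight to the drug-free period. Visit windows are ignored. The taper days below use the largest permitted steps.

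Days from EDV to FV = taper days + 14

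| Dose at EDV | Weekly taper steps (mg/day) | Days on drug after EDV | EDV to FV |
|---|---|---|---|
| No taper | none | 0 | 14 |
| 50 mg/day | 25 | 7 | 21 |
| 100 mg/day | 50, 25 | 14 | 28 |
| 150 mg/day | 100, 50, 25 | 21 | 35 |
| 200 mg/day | 150, 100, 50, 25 | 28 | 42 |

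The longest taper, 28 days, agrees with the protocol's stated maximum of 4 weeks. The range is therefore 14 to 42 days, of which 0 to 28 are on brivaracetam.

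**4. Detection lag**

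A urine test misses the most recent conceptions at both visits. With a common lag of *L* days, the conceptions that only the FV test would find fall between *L* days before the EDV and *L* days before the FV. The window keeps its length of 14 to 42 days but moves earlier. For *L* up to 14 days, the on-drug part becomes taper days + *L*, so the 0 to 28 days above understates it.

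**5. Chance per affected woman**

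The documents give neither the number of affected women nor a pregnancy rate. Assume 1 to 5 pregnancies per 100 subject-years.

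Chance ≈ (days / 365.25) × annual rate

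- Lowest: 14/365.25 × 0.01 = 0.00038, about 0.04%
- Full taper from the 100 mg/day starting dose: 28/365.25 × 0.01 = 0.0008 to 28/365.25 × 0.05 = 0.0038
- Highest: 42/365.25 × 0.05 = 0.00575, about 0.6%

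For scale, with assumed numbers of affected women: 20 women at 28 days gives about 0.015 to 0.08 expected pregnancies. Fifty women, all at the longest interval and highest rate, gives 50 × 0.00575 = 0.29.

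**The case against.** The strongest reply is that this is leftover bundling in one list item and not a decision to stop testing. Both schedules mark the test at the FV, and Protocol Amendment 1 had already separated it from the laboratory item at the minimal evaluation visits. Section 8.8 makes the test non-mandatory without forbidding it, so a test is missed only if a site follows the list over the schedule.

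There are also other safeguards:

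- Contraception is an eligibility condition, and women undertake to report a change in status (Sections 6.1.1 and 6.2.1).
- Section 10.2 requires an interim test whenever pregnancy is suspected.
- The FV still takes place, with adverse event reporting and a general health prompt.
- Serious adverse events are collected for 30 days after the subject's end of study, and those thought related to study drug are reportable without time limit. Miscarriage, ectopic pregnancy, fetal demise and congenital anomaly count as serious.

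The expected number is well below one even on unfavourable assumptions, and no analysis changes.

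These points are correct and limit the weight of the finding, but they do not remove it. Section 10.2 repeats the rule, so the bundling is not confined to one item. The safeguards act on a suspected pregnancy or on an adverse outcome that comes to light; an unsuspected, ongoing pregnancy at the FV passes through all of them. If the schedules show the intended design, that is a reason to correct Sections 8.8 and 10.2.

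**Conclusion.** The concern holds. Section 8.8, supported by Section 10.2, contradicts Tables 5-1 and 5-2. Following it drops the last scheduled check for an unsuspected exposed pregnancy because of laboratory results that have no bearing on pregnancy.

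The practical size is small. The group is limited to early discontinuers of childbearing potential with normal EDV results. The untested interval is 14 to 42 days, and the chance per affected woman is about 0.04% to 0.6%. The interval follows from the protocol's taper rules with visit windows ignored. The chance rests entirely on the assumed rate of 1 to 5 per 100 subject-years.

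The text conflict is certain. The harm is conditional on a site following Section 8.8 over the schedule. The plan should be corrected because the error is plain and the remedy is cheap; the study's objectives and analyses are not threatened.

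**What to change.** Keep the rule in Tables 5-1 and 5-2 and bring the text into line:

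- **Section 8.8:** take the urine pregnancy test out of the waived laboratory item and list it as a separate FV assessment, required for every woman of childbearing potential whatever the EDV results.
- **Section 10.2:** state that the waiver after a normal EDV does not apply to the pregnancy test.

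The cost is wording in two sections and one urine test per eligible woman at a visit that already takes place. The schedules already include the test, and site staff perform it without the central laboratory (Section 10.2). No SAP change is needed.

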8.9 Unscheduled Visit (all subjects)

At any time, the subject may have an additional study visit if the Investigator or the subject and/or legal representative deem it necessary. All information, including reason for visit, any information on AEs, etc, should be collected in the source documents and recorded in the appropriate sections of the eCRF.

If an Unscheduled Visit (UV) is conducted due to safety or efficacy reasons, a C-SSRS assessment will be performed with the subject during the visit. If a UV is conducted for reasons other than safety or efficacy concerns (eg, replacement of lost medication, repeated collection of a laboratory specimen due to collection or analysis issues), a C-SSRS will not be required at these visits.

9 ASSESSMENT OF EFFICACY

Efficacy variables will be assessed using the seizure count information recorded on the DRC.

At each visit, the subject will receive a DRC, to be filled in on days on which a seizure occurs, and to be returned at the next visit. No DRC will be dispensed at the UV or the FV.

The date, the symptom and the number of epileptic seizures will be recorded on the DRC, as well as individual description of seizures, intake of IMP, undesirable events with start and end dates, and changes in concomitant medication, if applicable.

The written information will be discussed with the subject at each visit in order to ensure completeness and accuracy. As a result of the discussion, the Investigator will assess the seizures according to the ILAE codes and record the seizure types and frequency on the DRC and eCRF; he/she will also confirm the presence of AEs (if applicable). The concomitant medication changes, healthcare provider consultations not foreseen per protocol, and AEs will be reported by the Investigator on the specific pages of the eCRF.

The DRC will be considered as source documentation. The subject should be educated to complete the DRC (eg, when taking evening tablets). Substantial noncompliance with DRC (seizures recording) may result in subject discontinuation from the study at any time by the Investigator or the Sponsor.

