12.3 Planned efficacy analyses

All efficacy outcomes will be summarized with descriptive statistics only on the FAS.

The 28-day adjusted seizure frequency will be calculated by dividing the number of partial seizures by the number of days for which the DRC was completed and multiplying by 28.

Planned efficacy analyses for rollover subjects in China and Japan include:

- Percent reduction in partial seizure frequency per 28 days from Baseline of EP0083 or N01358 to the Evaluation Period
- Responder rate in partial seizure frequency per 28 days over the Evaluation Period. A responder is defined as a subject with a $\geq 50\%$ reduction in seizure frequency from Baseline Period of EP0083 or N01358

Planned efficacy analyses for directly enrolled subjects in Japan include:

- Percent reduction in partial seizure frequency per 28 days from 8 weeks prior to BRV administration to the Evaluation Period
- Responder rate in partial seizure frequency per 28 days over the Evaluation Period. A responder is defined as a subject with a $\geq 50\%$ reduction in seizure frequency from 8 weeks prior to BRV administration

Planned efficacy analyses for all subjects (directly enrolled in Japan and rollovers in China and Japan) include:

- Seizure frequency per 28 days for partial seizures by 3-month periods over the Evaluation Period.
- Seizure frequency per 28 days for all seizure types (partial, generalized and unclassified epileptic seizure) by 3-month periods over the Evaluation Period.
- Percentages of subjects continuously seizure-free for partial seizure and all seizure types for at least 6 months and at least 12 months during the Evaluation Period.

- Seizure freedom (partial, all epileptic seizure) during the Evaluation Period.

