12.6 Handling of dropouts or missing data

Safety and efficacy variables will be analyzed as they are available. Days with missing information will be ignored in the calculation of the seizure frequency.

Since subjects will drop out at different times from the study, results will be presented by overall and by 6 month periods.

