### 3.2.6 Monthly time intervals

In terms of the analysis, a month is defined as 30 days and time intervals based on monthly durations are defined as a multiple of 30 days (eg, 12 months is defined as 360 days). The following definitions of 3-month intervals are based on 30-day months where the date of first dose of BRV is Day 1:

Interval	Duration Definition
3-month interval	
Month 1-3	Day 1-90
Month 4-6	Day 91-180
Month 7-9	Day 181-270
Month 10-12	Day 271-360

Subsequent 3-month intervals are defined in a similar manner. Three-month intervals will be used for analyses of efficacy (except for continuously seizure-free) and TEAE summaries.

For the analysis of efficacy outcomes, a subject is included in the analysis of a 3-month interval if the last dose of study drug during the Evaluation Period of EP0085 is equal or

greater than the last day of the 3-month time interval and the seizure diary was completed for at least 1 day during the 3-month interval over the Evaluation Period.

For TEAE summaries, a subject is included in the analysis of a 3-month interval if the last dose of study drug in whole period of EP0085 is equal or greater than the first day of the 3-month time interval (as N for the time interval) and with at least one specified TEAE within the 3-month interval (as n in the summary tables according to the AE onset date).

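### One Protocol 9 clause limits the seizure diary to seizure days, and the Full Analysis Set rule, read literally, drops subjects who never have a seizure: both are wrong as written

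*Protocol*

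**What the plan says.** **Diary instruction.** Protocol 9 says "At each visit, the subject will receive a DRC, to be filled in on days on which a seizure occurs". Elsewhere the protocol says daily. Table 5-1, footnote f (rollover subjects): "Seizure counts are collected on the subject's daily record card on a daily basis". Table 5-2, footnote e (direct enrollers): "After the EV, seizure counts are collected on the subject's DRC on a daily basis". The visit lists in Protocol 8.4 to 8.8 repeat this. Protocol 9 itself also has study-drug intake recorded on the card, suggests completing it with the evening tablets, and provides for a check: "The written information will be discussed with the subject at each visit in order to ensure completeness and accuracy". Protocol 7.7 requires compliance to be recorded at every intake.

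**Use of the diary.** Protocol 12.3 and SAP 8.1.1 obtain the 28-day frequency by "dividing the number of partial seizures by the number of days for which the DRC was completed" and multiplying by 28. Protocol 12.6 and SAP 4.1 add: "Days with missing information will be ignored in the calculation of the seizure frequency". To enter a 3-month interval, SAP 3.2.6 requires, among other things, that "the seizure diary was completed for at least 1 day during the 3-month interval over the Evaluation Period". SAP 8.1.4 requires at least 90% of diary days in the period to be non-missing before a subject can be called seizure-free.

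**Full Analysis Set.** Protocol 12.1 and SAP 3.5.3 require one dose and one or more seizure records on the diary during the Evaluation Period. All efficacy variables use this set, including seizure freedom over the Evaluation Period (SAP 8.2.4.2).

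**The concern.** Seizure frequency, responder rate and seizure freedom are the evidence for the secondary objective, maintenance of efficacy. Each needs days without seizures to be on record. A subject who follows the Protocol 9 clause leaves those days blank. A blank day then has to be classed as missing or as seizure-free, and neither document says what happens to a blank that the site has confirmed as seizure-free.

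The FAS wording raises a different problem. A rule that needs a seizure record, taken at its word, selects subjects on the outcome. It removes the subjects with the best possible result from the set on which that result is reported.

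**Working it through.** The documents give no figure to reproduce here. The check sets the texts against each other and applies the SAP formulas. Every diary pattern and percentage share below is an assumption chosen to show how the rule works.

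**1. Is the clause consistent with the rest?** No. Two schedule footnotes, five visit lists and the other instructions in Protocol 9 imply a card used every day. With twice-daily dosing and intake recorded on the card, a card left blank on every seizure-free day would break those instructions. The clause stands alone.

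**2. One partly blank diary.** Interval of 90 days (SAP 3.2.6); 3 partial seizures on 3 days; 57 days entered as zero; 30 days blank. Baseline 4 seizures in 56 days: 4/56 × 28 = 2.0.
- Blank = missing: completed days 3 + 57 = 60; 3/60 × 28 = 1.40; reduction (2.0 − 1.40)/2.0 = 30.0%, a non-responder.
- Blank = zero seizures: 3/90 × 28 = 0.93; reduction (2.0 − 0.933)/2.0 = 53.3%, a responder.

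**3. Clause followed strictly, blank = missing.** The completed days are then the seizure days. If all recorded seizures are partial, each completed day has at least one, so the 28-day frequency is at least 28. Direct enrollers enter with 1 to 7 partial seizures in 56 days (Protocol 6.1.3, criterion 10), a baseline of 1/56 × 28 = 0.5 to 7/56 × 28 = 3.5. The result is at least 28/3.5 = 8 times baseline. This is an extreme bound, and data review should catch it.

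**4. The 90% rule.** It needs 0.9 × 180 = 162 days for 6 months and 0.9 × 360 = 324 for 12 months.
- A seizure-free subject who writes only on seizure days has 0 of 180 if blanks are missing. That subject fails the rule and has a frequency of 0/0.
- If every blank counted as zero, the same subject would have 180 of 180. So would a subject who stopped writing at Day 90, and the rule would screen out nobody.

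Neither blanket rule works for cards kept under the clause.

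**5. The FAS read literally.** Whole-period freedom from all seizure types is 0% by construction. Whole-period freedom from partial seizures is possible only for a subject with some non-partial seizure. On the planned 217 subjects, with an assumed share free of all seizures throughout:

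| Assumed share | Excluded | Literal FAS | All-seizure freedom, all 217 | Literal FAS result |
|---|---|---|---|---|
| 2% | 4 | 213 | 1.8% | 0% |
| 5% | 11 | 206 | 5.1% | 0% |
| 10% | 22 | 195 | 10.1% | 0% |
| 20% | 43 | 174 | 19.8% | 0% |

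The responder rate would move too. With 87 assumed responders of 217 (40.1%), and all 22 excluded subjects in the 10% row being responders, it becomes (87 − 22)/195 = 33.3%.

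**6. What does the SAP mean by a seizure record?** SAP 3.2.6 asks for a diary day completed, SAP 8.2.3 for a seizure assessment, and SAP 8 bases all efficacy analyses on seizure records. The last must include zero-count days, or neither the frequency nor seizure freedom could be computed. All three point to any diary entry.

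**The case against.** The strongest reply is that little is undefined. A blank day is, on ordinary reading, not completed and therefore missing. Investigators review each card for completeness. SAP 4.1 implies that the Seizure Count form carries a not-done status. The broader FAS reading is the only one that makes the seizure-freedom endpoint meaningful, and Protocol 12.5 has a data evaluation meeting finalise the analysis sets before lock.

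Much of this stands, and it rules out three stronger readings that a reader might infer.
- *That the plan has no missing-day rule.* It has one, and a blank ordinarily falls under it. The gap is a day left blank as the clause instructs and then confirmed as seizure-free.
- *That seizure frequency in this study is inflated.* That would follow only if subjects obeyed the clause, the blanks were entered as missing, and the blank days had fewer seizures than the completed ones. The form is not shown, so none of this can be established.
- *That seizure-free subjects will be excluded.* Only the literal wording does this, and the rest of the SAP points the other way. Even literally, a subject with a 6- or 12-month seizure-free stretch and a seizure at another time stays in the FAS.

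What does not stand is leaving the text alone. The clause is a wrong instruction to subjects, and an analysis set should not have to be inferred from other sections or settled at a meeting after open-label data are visible.

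**Conclusion.** Both points hold as errors of wording. The Protocol 9 clause contradicts the other diary instructions and does not fit the frequency denominator or the 90% rule. The FAS rule, read literally, selects on outcome and fixes whole-period freedom from all seizures at 0%. Daily completion and a FAS based on any diary entry were probably intended.

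Whether the clause affected any data, and in which direction, cannot be known from the documents. The numbers above illustrate the rules and do not estimate bias. They rest on invented diaries and assumed shares of seizure-free subjects and responders. All summaries are descriptive, and the primary analysis of treatment-emergent adverse events is not touched. The correction is worth making because it costs almost nothing and the secondary objective rests on these variables.

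**What to change.** 1. **Protocol 9:** reword the clause so that the diary is completed every day, including days without a seizure.
2. **Protocol 12.1 and SAP 3.5.3:** define the FAS as at least one dose and at least one completed diary day in the Evaluation Period on or after first dose, with or without a seizure. If the protocol is not amended, record this in SAP 3.8, which now lists no changes.
3. **SAP 8.1.1 and 8.1.4:** define a completed day as a day with an entry, or a day confirmed as zero-seizure at the visit review and entered so on the Seizure Count form. Only unconfirmed blank days and not-done days are missing.

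The third change matters for cards already collected, which a protocol edit cannot repair. Classing every blank as missing would penalise subjects who followed the clause, even where the site had confirmed no seizures. Before adopting it, check that the form can show a confirmed zero.

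Cost: two protocol sentences and three SAP sections, or SAP 3.8 in place of 3.5.3. No new visit, procedure or analysis.
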